#### 9.1.7.3. Data Analysis for GBS etiology: Exploratory data mining-based signal detection

The statistical methods for this activity are described briefly below. Greater detail will be provided in the SAP.

#### 9.1.7.3.1. Data mining analyses and statistical methods

TreeScanTM software (www.treescan.org) will be used to analyze data via a self-controlled case-crossover design. In brief, the tree-based scan statistics use log-likelihood ratio tests to detect elevated frequencies of codes in electronic health data that have been grouped into a hierarchical tree structure and automatically adjusts for multiple overlapping scenarios inherent to data mining. The test statistic is computed via Monte Carlo hypothesis testing. Under the alternative hypothesis, there is at least 1 exposure, or group of exposures, for which there is a temporal cluster of GBS cases during some time interval in the observation window.

The important analytic information in the self-controlled case-crossover design using TreeScan is the time from the exposure to the outcome, within the prespecified observation window. The observation window for analysis (e.g., 84 days) is divided into a risk window and a comparison window. Both "fixed risk window" and "varying risk window" approaches are possible. In a fixed risk window analysis using TreeScan, these values are defined *a* 

priori (e.g., days -21 through -1 prior to GBS diagnosis as the risk window; days -84 through -43 as the comparison window). In a varying risk window analysis, the risk window is allowed to move within the overall observation window, while the comparison window varies accordingly and consists of all the days that are not in the risk window being evaluated. Exposure and GBS will not be permitted on the same day (day 0) because of the inability to distinguish the sequence of events within the same day in administrative claims data.

The self-controlled case-crossover design is compatible with the following 4 tree-based scan statistics: conditional and unconditional Bernoulli tree-based scan statistics for fixed risk window analyses, and conditional and unconditional tree-temporal analyses for varying risk window analyses. The specific statistic(s) that will be used will be specified in the final SAP.

Analyses will be performed with a threshold for statistical significance of p = 0.05 (1-sided).

#### 9.1.7.3.2. Statistical signal investigation

The TreeScan based analyses may find a statistical signal, suggesting a possible association between an exposure or group of exposures and GBS. However, false alarms are possible, and any statistical signal arising from these data mining analyses must be investigated with appropriately designed and controlled epidemiologic studies (outside the scope of this current protocol) rather than viewed, in and of itself, as evidence of causality. Where statistical signals cannot be ruled out (e.g., on the basis of obvious temporal confounding) or determined to be consistent with known associations, there may be an investigation using data summarized via the Patient Episode Profile and Retrieval (PEPR) tool. 40 PEPR summarizes information including diagnoses, procedures, and vaccines from administrative claims data for a specific window of time around an anchor of interest (e.g., GBS diagnosis). Signal investigation, if any, will be further described in the SAP.

#### 9.1.8. Quality Control

Please see Section 9.2.8 for quality control details for the full study.

#### 9.1.9. Limitations of the Research Methods for Research Question 1

#### 9.1.9.1. Limitations of GBS epidemiology and incidence

For this specific objective, the limitations are related to the nature of the data sources in general. Any study that utilizes administrative claims data is subject to misclassification. The GBS algorithm described in Table 1, which has been validated by others,  is expected to have a PPV of ~80%, meaning some of the incident GBS "cases" will not be GBS. Covariates of interest, such as certain antecedent and underlying conditions, may be misclassified due to under-capture of these conditions if they are not medically attended, diagnosed, and/or billed. Treatment of GBS in the hospital setting may be under-captured in claims data due to bundling of care. Vaccination status may be under-captured as participating national health plans do not have complete linkage with IIS sources and some IIS data may not be permissible to use for this project due to governance rules within the health plans. In addition, the COVID-19 pandemic affected healthcare utilization, and may have impacted rates of GBS.

# 9.1.9.2. Limitations of GBS etiology: Medical record review

There are potential limitations of the research methodology and data sources for this objective. First, members within the RPs, which are expected to be integrated delivery systems, may not be representative of the general population and findings from their data may not be representative of patient care in other settings.

PPVs will be calculated for the GBS algorithm overall and within important subgroups. Because stratified sampling will be done to ensure representation of the groups of interest, the PPV estimates may have wide 95% CIs. In addition, this study is not designed to calculate sensitivity or specificity of the algorithms.

Identification of the etiology of GBS, among those identified as confirmed or possible cases, may be challenging. Identifying antecedent infections or other preceding events requires documentation in the medical record, and diagnostic testing for many infections is uncommon. Clinician adjudicators may not have the information available to make the case and/or the etiologic determination.

# 9.1.9.3. Limitations of GBS etiology: Exploratory data mining-based scan statistics

Tree-based data mining is hypothesis generating and exploratory. Therefore, causation cannot be determined. Further, a tree organized around 1 characteristic (e.g., vaccine manufacturing platform or antigen content) may perform poorly if the outcome of interest is driven by a different characteristic (e.g., a specific adjuvant).

Like some other self-controlled methods, including the self-controlled case-crossover design, the method can be subject to time-varying confounding, including potentially by seasonality.

As noted above in Sections 9.1.9.1 and 9.1.9.2, vaccination status and antecedent infections may be under-captured. Another situation that may lead to a variable being under-captured is in the tie breaker scenario of multiple exposures within the same branch of the tree occurring on the same day (noted in Section 9.1.3.3.1). In this scenario, only the rarer exposure will be counted to give the rarer exposure more power. However, in practice, the tie breaker situation is rarely invoked. If it is invoked commonly in the conduct of this objective, a secondary analysis could select an exposure randomly as a sensitivity analysis.

#### 9.1.10. Other Aspects for Research Question 1

Not applicable.

#### 9.2. RESEARCH METHODS FOR RESEARCH QUESTION 2

Research Question 2: What is the risk of GBS after exposure to ABRYSVO among non-pregnant recipients 18-59 years of age at increased risk of RSV-LRTD?

#### Objectives:

• Signal detection: Among non-pregnant individuals 18-59 years at increased risk of RSV-LRTD, compare observed GBS case counts after ABRYSVO vaccination against expected GBS case counts via RCA.

• Signal evaluation: Among non-pregnant individuals 18-59 years of age, assess risk of GBS in the 21 or 42 days (depending on length of risk window) following ABRYSVO vaccination using a SCRI design.

#### 9.2.1. Study Design for Research Question 2

This PASS will implement a stepwise active safety surveillance approach for 4 RSV seasons in non-pregnant individuals 18-59 years at increased risk of RSV-LRTD. During initial stages of vaccination roll-out, an RCA using sequential surveillance methods will be the primary method for signal detection. Approximately 1 RCA will be conducted on the accumulating data per season for each of the 2 RCA study designs. If an RCA detects a statistically significant positive association between risk of GBS and ABRYSVO vaccination, or if 4 RSV vaccination seasons have completed without an RCA detecting a statistically significant finding of higher risk, a SCRI study will be conducted to allow for a more comprehensive assessment of the association of ABRYSVO exposure and GBS. If the RCA does not detect a statistically significant finding or reach a pre-specified number of GBS cases (to be specified in the SAP) by the end of 4 RSV seasons, inclusion of additional RPs or extending the length of the RCA study period will be considered. Once commenced, the SCRI study will use all data available at that time, which could include multiple RSV seasons.

# 9.2.1.1. Study Design for RCA

RCA is a method used to conduct population-based active surveillance of vaccine-related potential adverse events using electronic health data. Since 2005, it has been used by the CDC's Vaccine Safety Datalink (VSD) to monitor the safety of tetanus, diphtheria, pertussis (Tdap), measles, mumps, rubella, and varicella (MMRV), rotavirus, human papillomavirus (HPV), influenza, and coronavirus disease 2019 (COVID-19) vaccines. With this method, hypothesized exposure-outcome associations are evaluated using sequential methods under the null hypothesis that the vaccine does not increase the risk of the outcome. Sequential statistical analyses account for multiple testing of accumulating data. The goal of RCA is to detect potential safety problems as soon as possible while minimizing false positive signals.

Each RCA will be conducted on the accumulating data using 2 study designs, a historical comparator RCA and a concurrent comparator RCA. The first RCA will identify ABRYSVO vaccinees from October 2024 through October 2025; the subsequent 2 RCAs will be cumulative, using data starting from October 2024. Specifically, the second RCA will identify ABRYSVO vaccinees from October 2024 through October 2026, and the third RCA will identify ABRYSVO vaccinees from October 2024 through January 2028. GBS will be identified in the 21 days post-ABRYSVO vaccination, e.g., through November 2025 for the first RCA. GBS will also be identified 42 days post-ABRYSVO vaccination, but, for simplicity, an example timeline for 21-days post is presented below. Administrative claims data require time to accrue and approach completeness. Typically, it takes up to 6 months for ≥90% completeness in the inpatient setting. RP data refreshes with data quality checks that follow the Sentinel System processes take approximately 2 additional months. Below is an example of the anticipated timing for the first RCA:

- Identify ABRYSVO vaccinees from October 2024 October 2025
- Assess outcomes through November 2025
- Data through the end of November will have attained the 6-month lag at the beginning of June 2026. Thus, in June, RPs can begin building their datasets for data quality checks.
- RPs conduct data analysis on quality-checked data and provide results to HPHCI by early September 2026.

# 9.2.1.1.1. Study Design for Historical Comparator RCA

For the ABRYSVO-exposed group, ABRYSVO vaccinations from 22 October 2024 (the date of FDA approval of ABRYSVO for adults 18-59 years at increased risk of RSV-LRTD) through 21 days (for analyses using a risk window of 21 days) or 42 days (for analyses using a risk window of 42 days) prior to the most recent data available at the time of each RCA commencement will be included. Notably, although ABRYSVO has been FDA approved, insurance companies will likely not cover ABRYSVO for adults 18-59 years at increased risk of RSV-LRTD until after an ACIP recommendation, which is pending as of January 2025. Thus, ABRYSVO vaccinations in claims data will begin after the date of ACIP recommendation, not the date of FDA approval. However, for comprehensiveness and because IIS data may be available, ABRYSVO vaccinations will be included from the date of FDA approval onward.

For the comparator group, a background rate estimated from a historical vaccine-exposed group will be obtained. Historical comparators are routinely used in RCAs when evaluating rare outcomes because the expected outcome rates in the comparator can be generated using multiple years of prior data. The historical comparator group will consist of non-pregnant individuals 18-59 years of age at increased risk of RSV-LRTD who receive a comparator vaccine (mRNA COVID-19 or seasonal influenza vaccines) between 01 January 2017 and 30 September 2024 (for analyses using a risk window of 21 days) or 09 September 2024 (for analyses using a risk window of 42 days). These vaccine capture end dates are 21 and 42 days, respectively, prior to the US Food and Drug Administration (FDA) approval of ABRYSVO for adults 18-59 years at increased risk of RSV-LRTD. mRNA COVID-19 and seasonal influenza vaccines were selected as the comparator vaccines because these are adult vaccines that either do not or minimally increase risk of GBS (i.e., 0-2 attributable cases per million doses).

GBS will be identified from claims in all eligible individuals, using the algorithm specified in Table 1 during the specified follow-up time (follow-up time is defined in Section 9.2.3.2.1).

Confounding will be handled by using historical background incidence rates stratified by select covariates (described in Section 9.2.3.3.1 and 9.2.7.1.2).

# 9.2.1.1.2. Study Design for Concurrent Comparator RCA

Because the historical comparator group could be subject to secular trends in GBS, a concurrent comparator RCA will be performed among ABRYSVO-vaccinated individuals.

Using pre-defined risk and control windows (one analysis will use 1-21 days for risk and 43-84 days for control and another will use 1-42 days for risk and 43-84 for control; this timing is justified in Section 9.2.1.2) following ABRYSVO vaccination, and a time-based stratification approach, the risk of GBS will be evaluated based on the proportion of vaccinated individuals that are in the risk window at the time of the GBS event. A binomial variant of the maxSPRT will be used with a case-centered logistic regression approach. Additional advantages of this approach are that it does not need to restrict to a study population who meets the algorithm for increased risk of RSV-LRTD because these ABRYSVO-vaccinated individuals will be presumed to meet the indication, and it inherently adjusts for any seasonality trends.

# 9.2.1.2. Study Design for SCRI

There are 2 scenarios in which the SCRI study may be initiated: 1) if a statistically significant positive association between risk of GBS and ABRYSVO vaccination arises from any RCA, or 2) after 4 RCA seasons, if there was no risk detected. In the former scenario, the SCRI study will serve as refinement of the RCA finding, given the improved control of confounding with the SCRI design, to determine whether a true association exists.

The SCRI design is ideal for studying acute events (e.g., GBS) with well-defined risk periods after a transient exposure.  The incidence of events within a risk window is compared to the incidence of events within a control window. A strength of this design is its ability to control for time-invariant confounders, such as race and age. Time-varying confounders such as seasonality are not controlled unless explicitly accounted for in analyses.

The study population (detailed in Section 9.2.2.2) will be comprised of non-pregnant adults 18-59 years who received an ABYRSVO vaccination from 22 October 2024 (the date of FDA approval of ABRYSVO for adults 18-59 years at increased risk of RSV-LRTD) through the most recent data available at the time of the study commencement, which could include multiple RSV seasons.

The SCRI will compare incidence of GBS during a primary risk window of 1-42 days after ABRYSVO vaccination (day 0 is vaccination) with incidence of GBS during the primary control window 43-84 days after ABRYSVO. The 42-day risk window after vaccine administration for GBS is based upon recent studies that have found days 1-42 post-vaccination to contain the time of increased risk. A secondary risk window of 1-21 days and secondary control window of 43-84 days will also be studied in a sensitivity analysis.

GBS will be identified from claims in all eligible individuals using the algorithm specified in Table 1 during risk and control windows. If the SCRI study is triggered due to a statistically significant finding in the RCA, the GBS cases identified in claims will be confirmed via medical record review as part of the signal refinement process. If the SCRI study commences after 4 seasons without a signal in an RCA, the SCRI study will employ PPV-adjustment of the claims-identified GBS cases.

#### 9.2.2. Setting for Research Question 2

The source population for both the RCA and SCRI studies will be members from up to 3 national health plans; members from other appropriate data sources may be included. The participation of specific RPs will be noted in the final SAP.

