#### 9.2.7.2.2. Primary Data Analyses

A case-centered logistic regression approach will be used to analyze the data in this SCRI study. Incidence rate ratios with 95% confidence intervals (to estimate relative risk) and attributable risk with 95% confidence intervals per 100,000 doses and 100,000 person-years (to estimate absolute risk) will be calculated.

If the SCRI study is conducted after 3 RCAs (4 seasons) in the absence of a statistically significant finding of higher risk of GBS associated with ABRYSVO vaccination from an RCA, the study will employ PPV-adjustment of the claims-identified GBS cases using the PPVs produced in Research Question 1. If the SCRI study commences due to a statistically significant positive association between risk of GBS and ABRYSVO vaccination in an RCA, the GBS cases identified in claims will be confirmed via medical record review, where medical records could be retrieved. For GBS cases confirmed via medical record review, the date of GBS onset will be determined based on the clinician adjudicator, and the claims-based GBS date will not be used. GBS cases where medical records could not be retrieved will be adjusted based on the PPV of the GBS algorithm. For example, if medical records cannot be retrieved for 10 GBS cases and the PPV for the GBS algorithm is 80%, this will be readjusted to 8 GBS cases. A sensitivity analysis will restrict to chart-confirmed GBS cases.

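### After an RCA signal the SCRI re-uses the signalling cases with no stated allowance, so its rate ratio is biased upward when the true effect is null or modest

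*Protocol*

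**What the plan says.** Section 9.2.1.2 gives two routes to the SCRI: "if a statistically significant positive association between risk of GBS and ABRYSVO vaccination arises from any RCA", or "after 4 RCA seasons, if there was no risk detected". On the first route "the SCRI study will serve as refinement of the RCA finding", and its purpose is "to determine whether a true association exists". Section 9.2.1 adds: "Once commenced, the SCRI study will use all data available at that time, which could include multiple RSV seasons".

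The two analyses are close relatives. For the concurrent RCA (9.2.1.1.2), "A binomial variant of the maxSPRT will be used with a case-centered logistic regression approach"; for the SCRI (9.2.7.2.2), "A case-centered logistic regression approach will be used to analyze the data in this SCRI study". Sections 9.2.2.1.2 and 9.2.2.2 list the same six eligibility criteria. One of the two concurrent RCAs compares days 1-42 with days 43-84, which is the primary SCRI comparison.

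Section 9.2.7.2.2 reports the IRR and attributable risk with 95% confidence intervals. After a signal, cases are confirmed by chart and the adjudicator's onset date replaces the claims date. Cases without charts are scaled by the PPV. No allowance for the data-dependent start is stated, and no analysis of post-signal data only. The limitations in 9.2.9 do not mention that the RCA and SCRI share cases.

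**The concern.** A triggered SCRI is selected because the same data showed an excess. If that excess was chance, re-estimating it from the same cases carries the chance into the IRR and the attributable risk. Chart review removes misclassified cases, but not a chance excess among true ones.

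Section 9.2.1.2 justifies the SCRI by better confounding control. Against the 42-day concurrent RCA that argument is thin: the RCA already stratifies by calendar time, while 9.2.3.3.2 plans no covariates for the SCRI. What is at stake is the final report of a postmarketing requirement. A chance or weak signal could be presented as verified, with an inflated rate ratio, by the cases that raised it.

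**Working it through.** **1. How the SCRI was sized.** Table 6 assumes 2 cases per 100,000 person-years and windows of 21 and 42 days.
- Background per 21 days: 2e-5 × 21/365.25 = 1.15 per million. Ten excess cases per million give RR = 1 + 10/1.15 = 9.7, as stated.
- Single exact binomial test: null share 21/63 = 1/3, alternative share 9.7/(9.7 + 2) = 0.829. The smallest n with one-sided alpha ≤ 0.05 and power ≥ 80% is 7 (reject at 5 or more; alpha 0.045, power 0.90).
- Vaccinees: 7/(2e-5 × 63/365.25) = 2.03 million, against 2.0 stated.
- With unrounded RRs, the rows for 2, 3 and 5 excess cases also reproduce (29, 16, 11). The rows for 4 and 8 give 13 and 7 against 15 and 8.

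So the SCRI was sized as one fixed-sample test.

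**2. Scale for the primary 42/42 windows.** Expected null cases in 84 days at 9 million vaccinees: 9e6 × 2e-5 × 84/365.25 = 41.4. Conversely, 24, 50 and 100 cases correspond to 5.2, 10.9 and 21.7 million. Ten excess cases per million over 42 days is RR = 1 + 10/2.30 = 5.35.

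**3. Simulation.** Cases are Poisson, with three evenly spaced cumulative looks. The 42-day concurrent RCA has a flat log-likelihood-ratio boundary calibrated to one-sided 0.05. The SCRI is done at the first crossing, otherwise at look 3. The variations apply after a signal: 80% random chart retention, and extra data equal to one third of the planned total.

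No true effect. Upper-tail error is the chance, over both routes, that the lower 95% limit exceeds 1 (nominal 2.5%), with a likelihood-ratio interval:

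| Expected cases | SCRI data after signal | Upper-tail error | Median IRR given signal |
|---|---|---|---|
| 24 | identical | 5.2% | 3.8 |
| 24 | 80% retained | 3.8% | 3.8 |
| 24 | one third more | 2.4% | 2.1 |
| 24 | both | 2.0% | 2.1 |
| 50 | identical | 5.2% | 2.5 |
| 50 | 80% retained | 3.3% | 2.5 |
| 50 | one third more | 2.2% | 1.7 |
| 50 | both | 1.8% | 1.7 |

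At 9 million vaccinees, between these rows, the median IRR is about 2.9 on identical data. With both changes it is about 1.7; a repeat run gave 1.8. The apparent attributable fraction, 1 − 1/IRR, would be 1 − 1/2.9 = 66% and 1 − 1/1.7 = 41%, when the truth is zero.

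**4. Interval method.** On identical data, Wald and exact intervals give 2.8% and 2.4% at 24 expected cases, and 4.6% and 3.3% at 50. At 2,000 cases all three methods give 5.0 to 5.1%. With any of the four RCAs as trigger, the large-count figure is 4.7%.

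**5. Against the sizing level of one-sided 0.05.** An exact test gives 3.0 to 5.7% at 12 to 31 expected cases and at most about 7.1% at very large counts: 7.1/5 = 1.4 times. A likelihood-ratio test gives 7.4 to 8.3%, or 1.5 to 1.7 times.

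**6. True effects, identical data.** At RR 2 the median IRR after a signal is 2.9 (24 cases) and 2.3 (50). At RR 5.35 it is 5.0 and 5.2, so there is no upward bias.

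**The case against.** The strongest reply is that the protocol does not plan an SCRI on identical data. Charts are reviewed, onset dates are reset, and vaccinees accrued since the RCA cut can enter; footnote 4 of the milestones allows about 12 months from the reported finding to the final report. With later data the error inflation disappears. This stands. A reader might infer that the SCRI's false-positive rate is doubled, or that a false signal is almost always confirmed. The documents do not support either as a general statement. With a likelihood-ratio interval at 9 million vaccinees, a false signal from the 42-day concurrent RCA is followed by a CI above 1 in 100% of runs on identical data. That is close to automatic, because the RCA statistic is itself a likelihood ratio. It falls to 64% with chart loss, 42% with added data and about 30% with both.

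Three further points stand in part.
- The interval method is unstated and 9.2.7 leaves detail to the SAP, so the protocol cannot be faulted for a particular interval. The SCRI's inferential role, however, is fixed in the protocol itself.
- The historical RCAs use another comparator, risk-window cases only and the Table 3 subgroup, so the overlap there is partial.
- Section 9.2.9 says that a signal does not imply causality, and the protocol nowhere claims independent confirmation. But it offers the SCRI as the follow-up without disclosing the shared cases.

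On the other side, no minimum of post-signal data is guaranteed, and scaling unretrieved cases by a common PPV cancels from the rate ratio.

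**Conclusion.** The point holds as a problem of shared data and upward bias after a signal. With the 42-day concurrent RCA as trigger, 9 million vaccinees and no true effect, the median IRR is about 2.9 on identical data and about 1.7 to 1.8 with chart loss and one third more data. The attributable risk is biased with it. The bias is smaller at RR 2 and negligible at large effects such as RR 5.35.

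The error-rate part is secondary. About 5% against 2.5% is a ceiling, reached with identical data and either a likelihood-ratio interval or large counts. Wald and exact intervals are near or below nominal at most Table 6 sizes: five of its six rows need at most 4.6 million vaccinees. The exception is the 8.4 million row.

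These results assume even Poisson accrual, a flat boundary, an effect spread over days 1-42, random 80% chart retention and extra data of one third. Only the even spacing of looks is in the protocol, in Table 5. Less added data, or a crossing at the last look, would leave more bias.

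**What to change.** In 9.2.7.2.2, for a triggered SCRI, keep the ordinary IRR and 95% CI and report beside them:
- an estimate and interval that allow for the RCA trigger, for example a median-unbiased IRR with limits from the simulated or exact sequential distribution;
- a sensitivity analysis limited to vaccinees accrued after the signalling data cut.

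In 9.2.1.2 and 9.2.9, state that a triggered SCRI shares its cases with the RCA and is not independent confirmation.

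The cost is wording and computation on data the plan already collects, with no additional charts. The supplementary intervals will be wider, and the post-signal analysis may hold few cases, so it should be labelled supportive.
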